4.3.5 Planned sample size

The number of patients in this study is not based on statistical power considerations. The planned sample includes 20 patients which is the number believed to provide sufficient data to assess the potential of ^{99m}Tc-rhAnnexin V-128 to image disease severity in SpA patients and provide sufficient preliminary data to plan larger pivotal trials focusing on the confirmation of the benefit for this new imaging procedure for the early diagnosis of SpA.

At first, five patients will be recruited and analyzed as a Proof of Concept (PoC). In the PoC part of the study, medical images will be reviewed by the DMC in charge of assessing the imaging potential of ^{99m}Tc-rhAnnexin V-128 in terms of image quality, uptake and medical relevance. After reaching a consensus, the committee will decide if the clinical investigation should continue with the remaining 15 patients. The planned number of patients in the PoC study is not based on statistical considerations. However, this number of patients should provide sufficient relevant information for the evaluation of the images in terms of quality and medical relevance.

	MDL Modello	Area: 01 Documento: MDL 01.01 Revisione: 0 Data di revisione: 18/04/2013 Pagina: 27 di 85
	Statistical Analysis Plan	
ANNEXIN 03		

5 SUBJECT POPULATIONS (ANALYSIS SETS)

5.1 Efficacy

5.1.1 Full analysis set (FAS)

In accordance with the Intention To Treat (ITT) principle the FAS population includes all subjects who received the study drug and completed the ^{99m}Tc-rhAnnexin V-128 imaging procedure.

5.1.2 Per Protocol population (PP)

All subjects in the FAS population for whom no major protocol violations/deviations occurred. Deviations from the protocol including violations of the Inclusion/Exclusion criteria will be assessed as minor/major before the data base locking.

5.2 Safety set

The safety population is made up of all subjects who received the administration of ^{99m}Tc-rhAnnexin V-128.

5.3 Primary population

The primary, secondary [REDACTED] efficacy analysis will be based on the FAS population.

The primary efficacy analysis on the Primary endpoint of Phase II will be also performed on the PP population as confirmatory analysis. The analysis on the PP population will be performed if the size difference between this population and the FAS population exceeds 2 patients.

The assessment of safety and tolerability will be based on the Safety population.

	MDL Modello	Area: 01 Documento: MDL 01.01 Revisione: 0 Data di revisione: 18/04/2013 Pagina: 28 di 85
	Statistical Analysis Plan	
ANNEXIN 03		

6 STATISTICAL METHODS

6.1 Statistical analysis strategy

The statistical analyses will be performed in accordance with the principles of ICH E9 guideline and the guideline on clinical evaluation of diagnostic agents and they will be based on data from the study site, unless otherwise stated.

The statistical analysis will be performed by [REDACTED].

6.1.1 Efficacy endpoint

Due to the premature stopping of the study, the efficacy endpoints will not be addressed. All available efficacy data will be provided in subjects data listings and described in a descriptive manner in an abbreviated CSR.

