6.1.1.2 Primary endpoint of Phase II

The primary endpoint of Phase II is to determine the magnitude and dynamic range of ^{99m}Tc-rhAnnexin V-128 uptake in disease affected sacro-iliac or lumbar spine joints, in patients with clinical suspicion or confirmed diagnosis of Spondyloarthritis (SpA). SPECT/CT scans will be interpreted and graded by the P.I. and two independent experienced nuclear medicine physicians blinded from clinical data and other imagings modality results. Briefly, ^{99m}Tc-rhAnnexin V-128 uptake compared with background (e.g. physiological liver uptake) should be assessed for each affected area by nuclear medicine physicians using a 4-grade scoring system (0 = none, 1 = mild or present

[REDACTED]

	MDL Modello	Area: 01 Documento: MDL 01.01 Revisione: 0 Data di revisione: 18/04/2013 Pagina: 29 di 85
	Statistical Analysis Plan	
ANNEXIN 03		

but lower than background uptake; 2, moderate or equal to background uptake; 3, intense or greater than background uptake). The assessed uptake will be the score with more adjudications (two or more). In case of discrepancies among the three different readers, an adjudication process based on consensus should be put in place in order to obtain one final outcome for each area.

Imaging procedure result, SUV and uptake intensity grades for SPECT/CT of sacro-iliac and lumbar spine joints will be summarized in descriptive tables; furthermore, concordance between the raters will be assessed with Kendall's W. For both SPECT/CT, two separate analysis will be conducted: one based on values measured 60 min after IP injection and the other on values measured 120 min after IP injection.

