Statistical analysis: Imaging procedure result, SUV and uptake intensity grades for SPECT/CT of abdomen and of spot views, and imaging procedure result and uptake intensity grades for whole body planar imaging will be summarized in descriptive tables; furthermore, concordance between the raters will be assessed with Kendall's W. For each imaging assessment, two separate analysis will be conducted: one based on values measured 60 min after IP injection and the other on values measured 120 min after IP injection

	MDL Modello	Area: 01 Documento: MDL 01.01 Revisione: 0 Data di revisione: 18/04/2013 Pagina: 31 di 85
	Statistical Analysis Plan	
ANNEXIN 03		

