8 CHANGES FROM PROTOCOL

As per sponsor decision, it has been decided to close the study after the first 5 patients were enrolled. For this reason and due to the small number of patients enrolled, only subjects data listings will be produced for this study and the results described in a short close-out CSR.

	MDL Modello	Area: 01 Documento: MDL 01.01 Revisione: 0 Data di revisione: 18/04/2013 Pagina: 41 di 85
	Statistical Analysis Plan	
ANNEXIN 03		

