11 APPENDICES

11.1 Standard listings

All listings must contain examples of possible data and be presented in fixed font (arial) with a minimum size as 8.

	MDL Modello	Area: 01 Documento: MDL 01.01 Revisione: 0 Data di revisione: 18/04/2013 Pagina: 47 di 85
	Statistical Analysis Plan	
ANNEXIN 03		

Listing 16.2.1.1: Subject Disposition – All subjects

Subject ID	Screening date	Informed consent date	Visit 1 date	Phone call 2 date	Visit 3 date	Premature study discontinuation date	FAS	PP	Safety
PAT_PATNUMBER	PAT_FIRSTVISITDATE	PAT_INFCONS_DATE	PATV_VISITDATE	PATV_VISITDATE	PATV_VISITDATE	SD_DATE	[Derived Data]	[Derived Data]	[Derived Data]
03-US-001	11/03/2011	11/03/2011	11/04/2011	12/04/2011	11/05/2011		Yes	Yes	Yes
03-US-002	09/04/2011	09/04/2011	09/04/2011	10/04/2011	10/05/2011		Yes	Yes	Yes
03-US-003	10/07/2011	10/07/2011	15/07/2011	16/07/2011	NA	10/08/2011	Yes	No	Yes

Data Source Table: W_PATIENT, W_PATIENTVIS, W_SD.

Note: NA = Not Available for patient early withdrawal

File directory: *path of directory status from study level downwards* /XXXXXX.sas

	MDL Modello	Area: 01 Documento: MDL 01.01 Revisione: 0 Data di revisione: 18/04/2013 Pagina: 48 di 85
	Statistical Analysis Plan	
ANNEXIN 03		

Listing 16.2.1.2: Subject Disposition – Study Withdrawals

Subject ID	Screening date	Informed consent date	Premature study discontinuation date	Reason for withdrawal	Explanation	Notes	FAS	PP	Safety
PAT_PATNUMBER	PAT_FIRSTVISITDATE	PAT_INFCONS_DATE	SD_DATE	SD_OUTCOME	SD_OUTCOME_SP	SD_NOTES	[Derived Data]	[Derived Data]	[Derived Data]
03-US-001	11/03/2011	11/03/2011	10/05/2012	XXXXXX	XXXXXX	XXXXXX	Yes	No	Yes
03-US-002	09/04/2011	09/04/2011	10/05/2012	XXXXXX	XXXXXX	XXXXXX	Yes	No	Yes
03-US-003	10/07/2011	10/07/2011	10/05/2012	XXXXXX	XXXXXX	XXXXXX	Yes	No	Yes

Data Source Table: W_PATIENT, W_PATIENTVIS, W_SD.

Note: NA = Not Available for patient early withdrawal

File directory: *path of directory status from study level downwards* /XXXXXX.sas

	MDL Modello	Area: 01 Documento: MDL 01.01 Revisione: 0 Data di revisione: 18/04/2013 Pagina: 49 di 85
	Statistical Analysis Plan	
ANNEXIN 03		

Listing 16.2.1.3: Inclusion Criteria

Subject ID	Sex	Age	Screening date	Inclusion criteria			
				First (PoC phase)	First (Phase II study)	Second	Third
PAT_PATNUMBER	PAT_GENDER	PAT_AGEYEAR	PAT_FIRSTVISITDATE	IC_1A	IC_1B	IC_2	IC_3
03-US-001	Male	54	11/03/2011	Yes	Yes	No	Yes
03-US-002	Female	68	09/04/2011	Yes	Yes	Yes	Yes
03-US-003	Female	59	10/07/2011	No	Yes	Yes	Yes

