	MDL Modello	Area: 01 Documento: MDL 01.01 Revisione: 0 Data di revisione: 18/04/2013 Pagina: 54 di 85
	Statistical Analysis Plan	
ANNEXIN 03		

Listing 16.2.4.1: Demographics

Subject ID	Screening date	Sex	Date of birth	Partial date	Age	Ethnicity	Specify other ethnicity
PAT_PATNUMBER	PAT_FIRSTVISITDATE	PAT_GENDER	PAT_BIRTH_DATE	PAT_PARTIAL_BIRTH_DATE	PAT_AGEYEAR	PAT_ETHNIC	PAT_ETHNIC_SP
03-US-001	11/03/2011	Male	12/03/1959	Day	54	Other	XXXXXXXX
03-US-002	09/04/2011	Female	10/09/1945	Day & Month	68	Caucasian	
03-US-003	10/07/2011	Female	24/02/1954		59	Asian	

	MDL Modello	Area: 01 Documento: MDL 01.01 Revisione: 0 Data di revisione: 18/04/2013 Pagina: 55 di 85
	Statistical Analysis Plan	
ANNEXIN 03		

Listing 16.2.4.2/1: Disease Assessment

Subject ID	SpA diagnosis date	Partial date	Score of BASDAI	Score of BASFI	Score of BASMI	Score of MASES
PAT_PATNUMBER	DA_DATE	DA_PARTIAL_DATE	DA_BASDAI	DA_BASFI	DA_BASMI	DA_MASES
03-US-001	11/03/2011	Day	9.4	5.4	7.7	12
03-US-002	09/04/2011	Day & Month	5.2	6.7	0.5	10
03-US-003	10/07/2011		8.3	3.5	9.9	2

	MDL Modello	Area: 01 Documento: MDL 01.01 Revisione: 0 Data di revisione: 18/04/2013 Pagina: 56 di 85
	Statistical Analysis Plan	
ANNEXIN 03		

Listing 16.2.4.2/2: Disease Assessment

Subject ID	Was a MRI performed?	MRI date	Number of inflammatory joints	MRI results in		Clinical pain in		Category of patient treatment
				lumbar spine	sacroiliac joints	lumbar spine	sacroiliac joints	
PAT_PATNUMBER	DA_MRI_YN	DA_MRI_DATE	DA_MRI_NUM	DA_MRI_RES_LUM	DA_MRI_RES_SAC	DA_CLIN_PAIN_LU M	DA_CLIN_PAIN_SA C	DA_PAT_TRT
03-US-001	Yes	11/02/2011	2	Positive	Negative	No	Yes	Start of non-biologic DMARD
03-US-002	Yes	01/04/2011	3	Negative	Positive	Yes	No	Start of biologic DMARD
03-US-003	No	NA	NA	NA	NA	No	No	Change in NSAID therapy

	MDL Modello	Area: 01 Documento: MDL 01.01 Revisione: 0 Data di revisione: 18/04/2013 Pagina: 57 di 85
	Statistical Analysis Plan	
ANNEXIN 03		

Listing 16.2.4.3: Significant Medical History and Associated Pathologies

Subject ID	Medical condition	SOC	PT	Date of diagnosis	Partial date	Ongoing?	Currently treated?	Resolution date	Partial date
PAT_PATNUM BER	MH_MEDCOND	MEDDRA_SOC	MEDDRA_PT	MH_DIAGN_DA TE	MH_PARTIAL_S TART_DATE	MH_ONGOING_ YN	MH_TREATED_ YN	MH_END_DATE	MH_PARTIAL_E ND_DATE
03-US-001	XXXXXXXX	XXXXXX	XXXXXX	15/08/1990	Day	No		14/04/1994	Day
03-US-002	XXXXXXXX	XXXXXX	XXXXXX	31/12/2007	Day&Month	No		15/06/2008	Day&Month
03-US-003	XXXXXXXX	XXXXXX	XXXXXX	05/05/2005		Yes	Yes		

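### Does the missing link between the imaging *Result* and the three reader grades leave the efficacy listing of the five patients undefined?

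*SAP*

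**What the plan says.** SAP 6.1.1 sets the efficacy endpoints aside because the study stopped early, and then states: "All available efficacy data will be provided in subjects data listings and described in a descriptive manner in an abbreviated CSR". SAP Section 8 confirms the scope: "due to the small number of patients enrolled, only subjects data listings will be produced for this study", with a short close-out report.

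SAP 6.1.1.2 has SPECT/CT scans graded 0 to 3 by the principal investigator and two independent readers. For combining the three grades it says "The assessed uptake will be the score with more adjudications (two or more"), and where the readers differ, "an adjudication process based on consensus should be put in place in order to obtain one final outcome for each area". The same section names the outcomes: "Imaging procedure result, SUV and uptake intensity grades for SPECT/CT of sacro-iliac and lumbar spine joints will be summarized in descriptive tables". Section 6.1.1.3 has similar wording for planar images: "imaging procedure result and uptake intensity grades for whole body planar imaging will be summarized in descriptive tables". In both places the result and the grade stand side by side, with no derivation of one from the other.

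The shell for Listing 16.2.6.1 (SAP 11.1) has one *Result* column and three grade columns (PI, Reviewer 1, Reviewer 2). Four rows for mock subject 03-US-001 show *Positive* with grades 0, 0, 1: whole body planar and spot SPECT/CT, each at 60 and 120 minutes. Mock subject 03-US-002 has grades 2, 3, 2 and a blank *Result*. There is no column for the final grade. It is also absent from the five derived variables in SAP 11.4 (age, BMI, time from injection, adverse event duration, delay of onset).

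On the shells in general, SAP 11.1 says "All listings must contain examples of possible data". The shell headed "Listing 16.2.4.2/2: Disease Assessment" records MRI as positive or negative and pain as yes or no, for the lumbar spine and the sacroiliac joints.

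**The concern.** With listings as the only output, the imaging listing is the whole evidence base for the efficacy text. It carries two outcome fields that can disagree. In every mock row with a *Result*, the majority of the readers gave grade 0 (no uptake), yet the *Result* is *Positive*.

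If *Result* is what a reader sets beside the MRI and pain fields, two authors could take the same reads and report different numbers of positive patients. One would use *Result*, the other the majority grade. The study is open label and the five patients were already enrolled when this text was written, so a rule chosen at the writing stage might be chosen with the reads known. At stake is whether any statement on how many patients showed uptake would rest on a fixed definition.

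**Working it through.** **Inputs.** Three readers, grades 0 to 3 and the majority rule are from SAP 6.1.1.2. The example rows are from the Listing 16.2.6.1 shell. Five patients is from SAP Section 8. The documents give no cut-off for a positive image; those used below are assumptions to show the range.

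**Step 1. Apply the majority rule to the shell.** Grades 0/0/1 give final grade 0. Grades 2/3/2 give final grade 2. Both follow directly from the listed columns.

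**Step 2. Count the patterns the rule resolves.** There are 4 × 4 × 4 = 64 ordered patterns. For each grade, 1 pattern is unanimous and 3 positions × 3 other grades = 9 have exactly two readers agreeing, so 10 per grade and 4 × 10 = 40 with a majority. The remaining 64 − 40 = 24 (= 4 × 3 × 2) are three-way splits, which go to consensus.

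**Step 3. See where a positivity cut-off would matter.**

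| Final grade | Patterns | Final grade ≥1 | Final grade ≥2 | Any reader ≥1 |
|---|---|---|---|---|
| 0, all readers 0 | 1 | negative | negative | negative |
| 0, one reader above 0 | 9 | negative | negative | positive |
| 1 | 10 | positive | negative | positive |
| 2 | 10 | positive | positive | positive |
| 3 | 10 | positive | positive | positive |
| three-way split | 24 | consensus | consensus | positive |

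The two final-grade cut-offs agree on 1 + 9 + 10 + 10 = 30 of the 40 majority patterns and differ on the 10 with final grade 1. Adding the any-reader rule cuts full agreement to 1 + 10 + 10 = 21. That rule is not in the SAP, and the majority rule excludes it as a route to the final grade. These are counts of patterns, not probabilities.

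**Step 4. Size if a count were stated.** One patient in five is 1/5 = 20 percentage points. The exact (Clopper–Pearson) 95% limits are the 2.5% quantile of Beta(x, n − x + 1) and the 97.5% quantile of Beta(x + 1, n − x). For 3/5 (60%) they are 14.7% to 94.7%; for 4/5 (80%), 28.4% to 99.5%. An invented set with one area per patient (0/0/1, 1/1/0, 1/1/1, 2/3/2, 3/3/3) gives 4 of 5 at final grade ≥1 and 2 of 5 at ≥2. The extreme case, five patients all graded 0/0/1, gives 0 of 5 at any final-grade cut-off of 1 or more and 5 of 5 under the any-reader rule.

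**Step 5. Ask whether the mock cells show an intended rule.** Other SAP 11.1 shells contain values that cannot be taken literally:

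- Subject 03-US-001 is injected on 11/03/2011 at 10:50, and the 60-minute image carries the same date and time.
- For that subject the dose before injection, the residual dose, the injected dose and the volume are all 123.
- A 54-year-old is shown as failing the criterion of age over 18.
- The serious adverse event shell includes rows marked as not serious.
- The blood chemistry *Result* column holds units.
- Vital signs before injection and after imaging share one time and identical values.

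The four *Positive* rows are one placeholder pattern repeated for one mock subject. They are not four observations, and they do not show how *Result* will be assigned.

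**Step 6. Check the regions.** The four rows are planar and spot views. The majority rule sits under the primary endpoint, SPECT/CT of the sacro-iliac and lumbar joints. Those regions are covered in the shell only by its continuation row, and the listings index (SAP 10.1) gives them their own entries, 16.2.6.5 to 16.2.6.8.

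**The case for a change.** The strongest case for a change does not need the mock rows. The SAP treats *Result* as an outcome in its own right and never says who gives it or how it relates to the grade. The final grade, which the SAP does define, has no column, and a consensus grade for a three-way split cannot be rebuilt from the three listed grades. A descriptive account of five patients could easily slip into saying how many were positive, and the invented set above shows such a number moving from 4 to 2 of 5 with the cut-off alone. A clarification would be cheap.

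The missing definition and the missing column stand. The consequence does not follow from the plan. The SAP asks for no count of positives, and the comparison with MRI belongs to the endpoints it has set aside. A consensus grade, where one was reached, falls within the available efficacy data that 6.1.1 requires to be listed.

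The wording on discrepancies could be read as sending 0/0/1 to consensus, but the majority clause would then govern only unanimous reads, where nothing needs resolving. The natural reading is majority first and consensus for three-way splits.

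The worry about a rule chosen with the reads known is fair, but a cut-off written in now would also come after the five patients were enrolled. It would have to be labelled post hoc either way.

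**Conclusion.** No change to the plan. This is missing detail in a listing shell, together with careless placeholder values, in a closed five-patient study that reports listings and descriptive text only. Followed as written, the SAP shows all three grades per image, region and time point, and no stated rule produces a wrong result. A sensible author would describe uptake by the final grade, say where *Result* comes from, and call any positivity cut-off post hoc.

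The size is nil for the planned output. It would be 20 percentage points per reclassified patient only if the report chose to state a proportion, and at n = 5 that proportion would carry almost no precision.

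This rests on three assumptions: the close-out report keeps to the descriptive scope of SAP 6.1.1 and Section 8; consensus grades, where reached, are listed as available data; and *Result* is a field recorded at reading. Its definition may sit in redacted text or in the case report form, neither of which can be seen here.

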6.1.1.1 Primary endpoint of PoC

The PoC phase will assess the imaging potential of ^{99m}Tc-rhAnnexin V-128 in terms of imaging quality, disease-lesion radiotracer uptake and medical relevance to enable the decision-making to terminate or to continue the clinical investigation completing the enrollment with the remaining patients.

Parameters used by DMC to assess primary endpoint of PoC will be described in the DMC charter.

6.1.1.2 Primary endpoint of Phase II

The primary endpoint of Phase II is to determine the magnitude and dynamic range of ^{99m}Tc-rhAnnexin V-128 uptake in disease affected sacro-iliac or lumbar spine joints, in patients with clinical suspicion or confirmed diagnosis of Spondyloarthritis (SpA). SPECT/CT scans will be interpreted and graded by the P.I. and two independent experienced nuclear medicine physicians blinded from clinical data and other imagings modality results. Briefly, ^{99m}Tc-rhAnnexin V-128 uptake compared with background (e.g. physiological liver uptake) should be assessed for each affected area by nuclear medicine physicians using a 4-grade scoring system (0 = none, 1 = mild or present

[REDACTED]

	MDL Modello	Area: 01 Documento: MDL 01.01 Revisione: 0 Data di revisione: 18/04/2013 Pagina: 29 di 85
	Statistical Analysis Plan	
ANNEXIN 03		

but lower than background uptake; 2, moderate or equal to background uptake; 3, intense or greater than background uptake). The assessed uptake will be the score with more adjudications (two or more). In case of discrepancies among the three different readers, an adjudication process based on consensus should be put in place in order to obtain one final outcome for each area.

Imaging procedure result, SUV and uptake intensity grades for SPECT/CT of sacro-iliac and lumbar spine joints will be summarized in descriptive tables; furthermore, concordance between the raters will be assessed with Kendall's W. For both SPECT/CT, two separate analysis will be conducted: one based on values measured 60 min after IP injection and the other on values measured 120 min after IP injection.

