## **10.9 Analysis of efficacy**

### **Primary endpoint:**

In order to assess 99mTc-rhAnnexin V-128 magnitude and dynamic range of uptake within areas affected by inflammation, SPECT/CT scans will be interpreted and graded by at least two independent experienced nuclear medicine physicians blinded from clinical data and other imaging modality results. Briefly, 99mTc-rhAnnexin V-128 uptake compared with background (e.g. physiological liver uptake) should be assessed for each affected area by nuclear medicine physicians using a 4-grade scoring system (e.g. 0, none; 1, mild or present but < to background uptake; 2, moderate or = to background uptake; 3, intense or > to background uptake). In case of discrepancies between the different readers, an adjudication process based on consensus should be put in place in order to obtain one final outcome for each area.

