### ***13.3 Data Review***

All data relating to the study must be recorded in the e-CRFs provided by the Sponsor. These e-CRFs should always reflect the latest observations on the patient's participation in the study.

Therefore, e-CRFs are to be completed within 5 days after the patient's visit. To avoid inter-observer variability, every effort should be made to ensure that the study determinations are completed by the same individual who made the initial ones at baseline. The Investigator must verify that all data entries in the e-CRFs are accurate and correct.

The monitor will review the e-CRFs and evaluate them for completeness and consistency. The e-CRF will be compared with the source documents to ensure that there are no discrepancies between critical data. All entries, corrections and alterations are to be made by the responsible Investigator or his/her designee. The monitor cannot enter data in the e-CRFs.

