6.1.18 Role of independent data monitoring committee (DMC) / interim data review committee

The DMC consists of representatives of investigators and Sponsor representatives and could include external person such as independent experts, if judged appropriate by the Sponsor. The main function of the committee will be to review the images of the first 5 patients and determine if there is a premature high evidence of the presence of inadequate technical performance in this patients group. The DMC will also determine if there is a high evidence of an excess of adverse events.

The DMC will promptly give recommendations to continue or terminate the study. The DMC report will be edited by the Sponsor and sent to the ethics committee as well as competent authorities.

Preliminary results can be used by the Sponsor for publication purpose, before the end of the main trial.

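### The SAP gives the P.I., whose blinding is not assured, an equal third vote on the uptake grade that the protocol assigns to independent blinded readers, and does not record the change

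*SAP*

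**What the plan says.** Protocol 10.9, under the primary endpoint, assigns the reading to "at least two independent experienced nuclear medicine physicians blinded from clinical data and other imaging modality results". If they differ, a consensus-based adjudication is to give one outcome per area. The P.I. is not named as a reader.

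SAP 6.1.1.2 has the scans "interpreted and graded by the P.I. and two independent experienced nuclear medicine physicians blinded from clinical data" and from the results of other imaging. It then adds a voting rule that the protocol does not have: "The assessed uptake will be the score with more adjudications (two or more"). For the rest, it says: "In case of discrepancies among the three different readers, an adjudication process based on consensus should be put in place". It does not say who takes part in that consensus.

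The template for Listing 16.2.6.1 (Imaging Results, SAP 11.1) has three grade columns, for the PI, Reviewer 1 and Reviewer 2. It also has one Result column. It has no column for a final grade.

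Two other SAP sections limit what follows from this. Section 6.1.1 says that, because the study stopped early, the efficacy endpoints will not be addressed. The available efficacy data will be listed and described in an abbreviated CSR. Section 8 (changes from protocol) reports closure after five patients and restricts the output to listings. It does not mention the change of readers.

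**The concern.** The protocol protects the uptake grade in two ways: the readers are independent, and they do not know the clinical data or the other imaging. The SAP itself names the P.I. separately from the two independent physicians. So a reader whom it does not call independent now has a vote equal to theirs, whether or not the P.I. is blinded.

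Blinding is the second problem. If the blinding phrase covers only the two physicians, a grade from a reader who may know the pain sites and MRI enters the final grade. If it covers all three, the SAP states a property for which neither document describes a safeguard. Knowledge of pain sites matters here because secondary endpoint (a) counts a match between pain site and image abnormality as a true positive.

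At stake is whether the CSR's description of uptake can fairly be presented as the independent blinded read that the protocol specifies.

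**Working it through.** The plan gives no figure to reproduce. The sample size is not power-based, and neither document states a rate of reader agreement.

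**1. Is the P.I.'s blinding assured?** Four places bear on this.
- SAP 6.1.1.2: the blinding phrase follows the two physicians and may or may not reach back to the P.I.
- Protocol 13.3: "The Investigator must verify that all data entries in the e-CRFs are accurate and correct".
- SAP 6.1.9 and Listing 16.2.4.2/2: the recorded data include MRI result and clinical pain, each given separately for the lumbar spine and the sacro-iliac joints.
- Protocol 5.1: the study is single-centre and open label. No passage says how the P.I. would be kept from these data before grading.

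The P.I.'s blinding is therefore neither documented nor ruled out, and it is hard to square with the verification duty.

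**2. When does the P.I.'s grade count?** With four grades (0 to 3) and three readers there are 4 × 4 × 4 = 64 combinations.

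| Situation | Combinations | Outcome under SAP 6.1.1.2 |
|---|---|---|
| Independents agree | 4 × 4 = 16 | Their grade stands; the P.I. has no effect |
| Independents differ, P.I. matches one | 4 × 3 × 2 = 24 | The P.I. decides between their two grades |
| All three differ | 4 × 3 × 2 = 24 | Consensus, members not named |

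The P.I.'s grade comes into play in all 24 + 24 = 48 combinations where the independents differ. If the P.I. had no vote, it would come into play in none. These are counts of combinations, not probabilities.

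**3. How many areas?** The share in which the P.I. could play any part is 1 − (exact agreement of the independents). Assume agreement of 60–80%:
- 1 − 0.80 = 20%
- 1 − 0.60 = 40%

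For five patients and two regions (lumbar spine, sacro-iliac) there are 5 × 2 = 10 area reads at each time point. The expected number affected is 10 × 0.20 = 2 to 10 × 0.40 = 4. If areas are treated as independent, the chance of at least one is 1 − 0.80^10 = 89% to 1 − 0.60^10 = 99%.

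**4. How far could grades move?** Take an extreme case: the independents differ by exactly one grade, and the P.I. always sides with the higher rather than with either at random. The mean grade then rises by (disagreement rate) × (1 − 0.5), which is 0.20 × 0.5 = 0.10 to 0.40 × 0.5 = 0.20 of a grade.

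**5. What output carries the effect?** The listing prints the three grades separately, so it does not hide the P.I.'s contribution. Two places remain. One is the CSR text, because SAP 6.1.1.2 holds the SAP's only rule for a final grade. The other is the Result column, whose source is not stated. A placeholder row in the template pairs grades 0/0/1 with a positive Result. It is dummy data and proves nothing about the study, but the template gives no rule linking Result to the grades.

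**The case against.** A reader might go further and infer that the P.I. cannot be blind. The documents do not support that.
- The blinding phrase can be read as covering all three readers.
- SAP 6.1.1.2 says uptake "should be assessed for each affected area by nuclear medicine physicians using a 4-grade scoring system", which fits a P.I. who is an imaging physician.
- The synopsis lists more than one investigator. A rheumatologist informs patients (Protocol 13.12) and is told of imaging anomalies (8.5), so the clinical work-up may lie elsewhere.
- Protocol 13.3 lets a designee make eCRF entries and sets no timing for verification relative to image reading.
- The SAP states that "The DMC consists of representatives of investigators and Sponsor representatives", but such representatives need not include the P.I., and neither document says that the committee sees pain sites or MRI.

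A reader might also infer that the SAP bypasses a blinded consensus between two readers. Protocol 10.9 allows more than two readers, and does not say that the consensus is blinded or limited to two people. A third reader is therefore not in itself a breach.

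Finally, the P.I.'s vote might be thought to settle the primary endpoint. That describes the planned Phase II analysis, which SAP 6.1.1 and section 8 have set aside. The listing also already separates the P.I.'s grade.

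These replies limit the point but do not remove it. The added reader is not described as independent, has an equal vote and no documented blinding, and is missing from the SAP's record of changes. SAP 6.1.1 still requires the efficacy data to be described.

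**Conclusion.** The point holds in limited form. The SAP departs from the protocol's independent read by giving the P.I. an equal vote, does not record this in section 8, and leaves the P.I.'s blinding unassured. When the two independents differ, the P.I. either chooses one of their grades or the area goes to an undefined consensus. Under the majority rule the P.I. cannot impose a grade that neither independent gave.

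The size is unknown. The 20–40% rests on assumed agreement of 60–80% and is a ceiling on areas where the P.I. could play any part. It should not be read as the share that the P.I. decides. The count of 2 to 4 areas per time point further assumes two regions per patient.

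With no efficacy endpoint analysed, the practical effect is confined to the CSR's descriptive account of uptake and to the Result column. It merits correction because the remedy is cheap and, with five patients, a few grades can change a description.

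**What to change.** - In SAP 6.1.1.2, take any final grade from Reviewer 1 and Reviewer 2, with consensus between those two when they differ. This meets Protocol 10.9 and also names who takes part in the consensus.
- Base the CSR's description of uptake, and any statement on reader concordance, on the same two readers.
- Keep the P.I. grade as its own column in Listing 16.2.6.1, labelled 'P.I. read, not used for the final grade'. State the P.I.'s actual blinding status and, if blinded, how this was achieved. Do not label it unblinded by assumption.
- State the source of the Result column.
- Record the change of readers in SAP section 8.

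The cost is SAP wording and a column label, with no new readers or scans. The small downside is that a few areas that a majority would have settled need a consensus discussion between the two independent readers.
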